13.2. ANALYSIS OF LABORATORY PARAMETERS

Summary statistics of blood laboratory data will be provided along with summary of the change from preoperative assessment, calculated for continuous variables as difference of values (section 18.2).

The percent of subjects with results within the lab normal values at each time interval will be calculated (normal reference limits provided by the sites). In addition, shift tables of values within normal ranges from preoperative to annual post-operative FU assessment will be generated by treatment group.

13.3. PLATELET COUNT AND CKMB DETERMINATION

Platelet count and CKMB/troponin will be analyzed by means of summary statistics (section 5.2) and box plots at preoperative and at each determination, overall and for each treatment arm.

13.4. PACEMAKER EVALUATION

For all patients who will have been implanted with a permanent pulse generator, all ECG Core Lab parameters will be descriptively analyzed by visit and treatment arm.

14. SUBGROUP ANALYSIS

The following analyses will be repeated for each subgroup (see section 5.3) using the same analysis population planned for each analysis:

- Subject disposition (section 0)

- Subject demographics (section 8.1), Implant characteristics (section 8.2), Valve characteristics (section 8.3), CT Scan (section 8.4), other baseline characteristics (section 8.6), and Healthcare Economics (section 8.8).
- Primary Endpoint (section 10).
- Forest plot showing the hazard ratio and 95% confidence intervals associated with variables considered in the multivariate analyses (treatment arm and all variables listed in section 5.3) with time to the primary endpoint (MACCE) as the dependent variable.
- Adverse Events (section 13.1)

TFLs will report per each subgroup level the overall and by treatment results. Analysis by subgroup will be performed if each subset has at least 15% of the allocated subjects.

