5.3. SUBGROUPS DEFINITIONS

The following variables and levels will be considered for subgroup analyses:

- Gender (“Female” vs “Male”)
- Surgical approach (“Full sternotomy” vs “Mini-sternotomy”)
- Concomitant procedures (“Concomitant procedure” vs “Isolated procedure”)
- STS predicted risk of mortality (“Low risk [<4]” vs “Med/High risk [≥ 4]”)
- Regurgitation severity (“None/Trace” vs “Mild/Moderate/Severe”) at discharge
- Early (≤ 30 days) Post-implant permanent PaceMaker (“Yes” vs “No”)

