10.3. PRIMARY ANALYSIS

The primary analysis will calculate the Bayesian posterior probability that the difference [$MACCE_{CONTROL} - MACCE_{PERCEVAL}$] is lower than 0.05 (predetermined non-inferiority margin):

$$\Pr(MACCE_{CONTROL} - MACCE_{PERCEVAL} < 0.05 \mid \text{Data})$$

The null hypothesis will be rejected, and non-inferiority concluded, if the posterior probability exceeds 0.9775 at the final analysis. This threshold was selected based on simulations to control the Type I error rate at 2.5% one-sided (CIP Appendix 8).

The probability $\Pr(MACCE_{CONTROL} - MACCE_{PERCEVAL} < 0.05 \mid \text{Data})$ is calculated on the basis of simulation after the definition of the posterior distribution of p_j according to the following steps:

1. The number of responders X_j is modeled in arm j as $X_j \sim \text{Binomial}(n_j, p_j)$ where n_j is the number of subjects for arm j and p_j is the proportion of subjects that are event-free at one year (response rate);
2. The response rates p_j are then transformed and modeled independently on the log-odds scale. They have a Normal prior distribution:

$$[\theta_j] = \left[\log \left(\frac{p_j}{1 - p_j} \right) \right] \sim N(\theta_0, \sigma_0^2)$$

with $\theta_0 = 1.99$ and $\sigma_0^2 = 3^2$ so that when converted back to the probability scale, this prior is centered at 0.88 (the expected event-free rate for the control arm);

3. One million (1000000) posterior samples for p_j in each arm will be drawn using a standard Markov chain Monte Carlo (MCMC) technique (random walk Metropolis-Hastings algorithm) after discarding the initial set of burnin samples. The calculation of the probability $\Pr(\text{MACCE}_{\text{CONTROL}} - \text{MACCE}_{\text{PERCEVAL}} < 0.05 \mid \text{Data})$ will be done as

$$\frac{\#\text{times} [\text{MACCE}_{\text{CONTROL}} - \text{MACCE}_{\text{PERCEVAL}} < 0.05]}{1000000}$$

In case of test for superiority, the Bayesian posterior probability of superiority

$$\Pr(\text{MACCE}_{\text{CONTROL}} < \text{MACCE}_{\text{PERCEVAL}} \mid \text{Data})$$

will be assessed in the Per Protocol population and will be provided. Superiority will be claimed if the above probability exceeds 0.9775. In order to calculate the probability of superiority, one million (1000000) simulations will be run using the posterior distribution on p_j in each arm, and the calculation of the probability $\Pr(\text{MACCE}_{\text{CONTROL}} < \text{MACCE}_{\text{PERCEVAL}} \mid \text{Data})$ will be done as

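### Subgroup section re-runs the primary analysis, with its 0.9775 rules, in every level of six factors but never assesses whether the Perceval effect differs between levels

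*SAP*

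**What the plan says.** SAP 5.3 defines six two-level factors: gender, surgical approach, concomitant procedures, STS risk, regurgitation severity at discharge, and permanent pacemaker within 30 days. That makes up to 12 subsets. SAP 14 then states: "The following analyses will be repeated for each subgroup (see section 5.3) using the same analysis population planned for each analysis". One listed item is the primary endpoint, with a reference to section 10 as a whole.

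Section 10 is the full testing section. Its rule for non-inferiority (margin 0.05) is: "The null hypothesis will be rejected, and non-inferiority concluded, if the posterior probability exceeds 0.9775 at the final analysis". Its rule for the nested superiority test is: "Superiority will be claimed if the above probability exceeds 0.9775". It also contains the sensitivity analyses with their own pass criteria.

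The only restriction on subgroup work is size: "Analysis by subgroup will be performed if each subset has at least 15% of the allocated subjects".

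The planned graphic is a "Forest plot showing the hazard ratio and 95% confidence intervals associated with variables considered in the multivariate analyses", the variables being "treatment arm and all variables listed in section 5.3", with time to MACCE as the outcome. Protocol 10.7 leaves subgroup analysis entirely to the SAP.

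**The concern.** A subgroup analysis should answer one question: does the effect of Perceval against a stented valve differ between kinds of patient? That requires comparing the effect across levels. SAP 5.3, 10, 11 and 14 and protocol 10.1 and 10.7 contain no treatment-by-subgroup term. The only interactions with treatment anywhere are treatment by log time, as a proportional-hazards check (SAP 11), and treatment by time in the EQ-5D model (SAP 12.3).

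The plan does supply a decision rule sized for the whole trial and points it at subsets as small as 15% of subjects. A subset can miss that rule through lack of information alone. A dozen looks at the superiority rule can also produce a positive by chance. A trial that meets its primary objective could then be reported with several subgroups where non-inferiority was not shown, and nothing in the plan would tell the reader whether that reflects the valve or the subset size. The SAP's reason for not adjusting alpha (10.2) covers one hierarchical sequence, not up to 12 in parallel. Elsewhere the SAP does attend to multiplicity: section 8 applies a Bonferroni correction to about 100 baseline comparisons.

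**Working it through.** **Inputs from the documents.** Margin 0.05 and threshold 0.9775 (SAP 10.2, 10.3); 91% event-free in both arms and a maximum of 1234 subjects (SAP 2.3); 1:1 allocation (SAP 2.4); 10% attrition to the per-protocol set (protocol 10.3); 15% minimum subset (SAP 14). Per-protocol subjects per arm: 1234 × 0.9 / 2 = 555.

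**Reproducing the plan's power.** P(meet rule) = Φ(0.05 / √(2p(1−p)/n) − 2.005), where 2.005 is the normal quantile of 0.9775.

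- p = 0.91, n = 555: SE = √(0.1638/555) = 0.0172; Φ(2.910 − 2.005) = 0.82. SAP Table 1 states 0.805.
- p = 0.88, n = 555: SE = √(0.2112/555) = 0.0195; Φ(2.563 − 2.005) = 0.71. SAP Table 1 states 0.704.

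Both are within two percentage points, so the formula is adequate for subsets.

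**One subset, arms truly equal at 91%, N = 1234.**

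| Share of subjects | n per arm | SE | 0.05/SE − 2.005 | P(meet rule) |
|---|---|---|---|---|
| 85% | 472 | 0.0186 | 0.68 | 0.75 |
| 50% | 278 | 0.0243 | 0.06 | 0.52 |
| 30% | 167 | 0.0313 | −0.41 | 0.34 |
| 15% | 83 | 0.0444 | −0.88 | 0.19 |

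As a check, the SAP's own posterior (Normal(1.99, 3²) prior on the log-odds, every pair of binomial counts enumerated) gives 0.52, 0.35 and 0.21 for the last three rows. The approximation is only slightly pessimistic in the smallest subset. If accrual stops at 900 (405 per arm), the formula gives 0.40, 0.26 and 0.15.

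**All subsets together.** The documents give no subgroup prevalences, so the splits and the independence of the factors are assumptions. Each row is 3,000 simulated trials at a fixed N, with equal arms at 91% and 10% attrition.

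| N | Factors and splits | Any subset misses NI | Same, given overall NI | Mean number missing, given overall NI | Any false superiority |
|---|---|---|---|---|---|
| 1234 | four, all 50/50 | 88% | 85% | 3.0 of 8 | 12% |
| 1234 | six, all 50/50 | 91% | 89% | 4.6 of 12 | 15% |
| 1234 | six: two 50/50, three 30/70, one 15/85 | 98% | 98% | 4.9 of 12 | 17% |
| 1234 | six, all 85/15 | 99.8% | 99.8% | 5.3 of 12 | 16% |
| 900 | six, all 85/15 | 99.9% | 99.9% | 5.7 of 12 | 18% |

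If only one factor passed the 15% gate, at least one of its levels would miss the rule in 73% (50/50) to 85% (85/15) of trials at N = 1234. The superiority column is plausible: eight independent looks would give 1 − 0.9775⁸ = 17% and twelve 1 − 0.9775¹² = 24%. The simulated rates are lower because the subsets overlap.

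**What the alternative can do.** Take a 5-point difference in treatment effect across a 50/50 split at N = 1234. The SE of the interaction is √2 × 0.0243 = 0.0343, so two-sided power at 0.05 is about Φ(0.05/0.0343 − 1.96) = Φ(−0.50) = 31%. With no true heterogeneity, unadjusted tests treated as independent give at least one false signal with probability 1 − 0.95⁴ = 19% for four factors, or 1 − 0.95⁶ = 26.5% for six.

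**The case against.** The fair reply has four parts.

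First, the SAP never says that non-inferiority or superiority will be declared in a subgroup. Section 14 lists the primary endpoint beside disposition and demographics and describes the outputs as tables by subgroup level and treatment. A reader might infer that subgroup claims are intended, but the documents do not say so. What stands is that section 10 is repeated without restriction and nothing switches its decision rules off.

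Second, the forest-plot item sits in the list of analyses to be repeated per subgroup, so it could be read as giving a Perceval hazard ratio within each level. A literal repeat of section 10 would also give Kaplan-Meier and Bayesian estimates by level, and the list of outputs is in a separate document (SAP 3.2). It is therefore too strong to say that within-level effects cannot appear. As written, however, the plot shows the terms of one multivariate model, and on either reading the levels are never compared.

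Third, a posterior below 0.9775 in a small subset is inconclusive, not a wrong result, and the SAP does not call it failure. The percentages also depend on splits that the documents do not give. This limits the wording but leaves the single-subset rates unchanged.

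Fourth, interaction tests are weak and bring their own false signals: 19% for four factors, above the 12% for false superiority with four 50/50 factors. They would also be unsound for regurgitation at discharge and early pacemaker, which arise after implant. Both points stand and shape the fix.

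**Conclusion.** The point holds as a gap in the SAP. The primary-endpoint rules carry into every subset unqualified, and differences in the Perceval effect between levels are never assessed. The second part follows from the text alone and needs no assumption.

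The size does rest on assumptions: equal arms at 91%, 10% attrition, independent factors and assumed splits. At N = 1234 a subset meets the non-inferiority rule about 52%, 34% or 19% of the time at 50%, 30% or 15% of subjects. With four to six qualifying factors, 85% (four at 50/50, given overall non-inferiority) to 99.8% of trials show at least one subset missing it. A false superiority result appears in 12% to 17% of trials at N = 1234, and up to 18% at N = 900.

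A reader might go further and call false subgroup failures near certain. The lower end of the range, the unknown prevalences and the 15% gate do not support that in general. The primary conclusion of the trial is not affected; what is at risk is the interpretation of the subgroup results.

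**What to change.** In SAP 14:

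- State that subgroup results are exploratory and that no non-inferiority or superiority decision is made within a subgroup.
- For the four baseline factors (gender, surgical approach as planned at randomisation, concomitant procedure as planned, STS risk), fit treatment, factor and their interaction. Use the risk difference for one-year MACCE and a Cox model for time to MACCE.
- Replace the forest plot with the Perceval-versus-control risk difference and hazard ratio, with 95% confidence intervals for each level and the interaction p-value.
- Present regurgitation at discharge and early pacemaker descriptively only. They arise after randomisation and implant, so comparisons within their levels are not protected by randomisation.
- Record the limits: about 31% power for a 5-point difference in effect across a 50/50 split, and about a 19% chance of any false signal from four unadjusted tests at 0.05. Estimates with intervals should therefore be the main display.

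The cost is SAP wording and a different plot. No new data are needed, provided the database records whether a concomitant procedure was planned; the documents do not confirm that field. The change should be made before the primary analysis is run.

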15. INTERIM ANALYSIS

Two interim analyses will be performed to select the sample size. These interims will be triggered when the number of subjects enrolled will be approximately 900 and 1050 (interim analyses cut-off dates). The study will stop accrual for expected success if the posterior probability of non-inferiority in the PP population is sufficiently high. The threshold varies by interim: accrual will stop if the posterior probability exceeds

- 0.996 at N=900, or
- 0.993 at N=1050.

The analysis will be conducted by the external Independent Statistical Unit who will communicate to the Sponsor the result of the interim analysis and the consequent decision on the continuation of enrollment (i.e. “Stop enrolment for predicted success”, “Continue enrolment”).

As the interim analyses will only determine whether accrual needs to be stopped, then the interim analyses decisions have no impact on the subsequent study conduct. Therefore subject follow up will continue up to 5 years and the primary analysis will take place at the 12-month primary analysis.

At the time of each interim analysis, there will be subjects eligible for Per Protocol analysis population whose one-year outcome is unknown (e.g. ongoing subjects not having yet reached the one-year visit). For this reason at the interim analysis an imputation model will be used for their one-year outcome according to these rules:

- Any subjects that are missing the one-year outcome, but are known to have a MACCE event at an intermediate time point, will have their one-year outcome imputed as “not MACCE-free”.
- Any subjects that are missing the one-year outcome but have not had a MACCE event at an intermediate time point (3, 6, and 9 month intervals) will have their one-year outcome imputed, using multiple imputation. The probability that a subject remains MACCE-free at one year, conditional on being MACCE-free as of their last known intermediate time point (3, 6, and 9-month intervals), follows a Beta-Binomial distribution. A non-informative Beta(1,1) priors, separately within each arm is going to be applied. Additional details are provided in the CIP Appendix 8.

16. ABBREVIATIONS

Table 6 : List of abbreviations and acronyms

Acronym	Verbatim
AE	Adverse Event
ANCOVA	Analysis of Covariance
AVR	Aortic Valve Replacement
CEC	Clinical Event Committee
CI	Consumption Index
CIP	Clinical Investigation Plan
CM	Concomitant Medication
CT-Scan	Computerized Tomography Scan
DSMB	Data Safety Monitoring Board
DVI	Doppler Velocity Index
EC	Ethics Committee
ECG	Electrocardiogram
eCRF	electronic Case Report Form
EDC	Electronic Data Capture
ENR	Enrolled population
EOA	Effective Orifice Area
EOAi	Effective Orifice Area index
EQ-5D-5L	European Quality of Life - 5 Dimensions – 5 Levels
ICH	International Conference on Harmonization
ICU	Intensive Care Unit
ITT	Intention To Treat
LV	Left Ventricle
LVEF	Left Ventricle Ejection Fraction
LVOT	Left Ventricle Outflow Tract
M1	1 month assessment (EQ5D)
M3	1 to 3 months FU visit
MACCE	Major Cerebral And Cardiovascular Event
MI	Multiple Imputation

Acronym	Verbatim
MICS	Minimal Invasive Cardiac Surgery
mITT	modified Intention To Treat population
MMRM	Mixed Model for Repeated Measures
MPG	Mean Pressure Gradient
mRS	modified Rankin Scale
NCI	Normalized Consumption Index
NIHSS	NIH Stroke Scale/Score
NYHA	New York Heart Association
PM	Pace Maker
PP	Per Protocol population
PPG	Peak Pressure Gradient
PPI	Permanent Pacemaker Implant
QALY	Quality Adjusted Life Years
QoL	Quality Of life Questionnaire
SAE	Serious Adverse Event
SAF	Safety population
SAP	Statistical Analysis Plan
STS	Society of Thoracic Surgeons
SVD	Structural Valve Deterioration
TAVI	Transcatheter Aortic Valve Implantation
TEAE	Treatment Emergent Adverse Event
TFL	Table, Figures and Listings
TTE	Trans Thoracic Echocardiogram
USADE	Unanticipated Serious Adverse Device Effect
VARC	Valve Academic Research Consortium
Y1 (Y2,Y3,Y4,Y5)	1 (2,3,4,5) year(s) FU visit

18. ANALYSIS SPECIFICATIONS

The purpose of this section is to give technical details for the implementation of the SAP.

18.1. PERCENTAGES AND DECIMAL PLACES

If not otherwise specified, the following rules are applied:

- Percentages are presented to 1 decimal point.
- Percentages equal to 0 or 100 are presented as such without a decimal point.
- For descriptive summary statistics, the same number of decimal places as in the raw data are presented when reporting minimum and maximum values, 1 more decimal place when reporting mean, median, quartiles and confidence interval (CI) and standard deviation (SD).
- P-values are presented to 3 decimal points. P-values < 0.001 will be reported as such.
- Ratios are presented to 3 decimal points.

The above described displaying rules must not be changed (e.g., rounding) for the CSR text and are used 1:1 in the body report as well.

18.2. PRESENTATION OF DIFFERENCES AND CHANGES

If not differently indicated:

- for differences between active and comparator, active will constitute the minuend and comparator the subtrahend. For differences between active comparator and placebo the active comparator will constitute the minuend and placebo the subtrahend;
- for changes from baseline the baseline value will constitute the minuend and the later value the subtrahend.

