11.2. SITE REPORTED ECHOCARDIOGRAPHIC DATA

11.2.1. Hemodynamic data

Mean changes from baseline in site-reported valve hemodynamic

- mean gradient,
- peak gradient and
- LV mass

will be analyzed based on data observed while the subject remains on study (observed cases) as well as data imputed using multiple imputation (MI) methodology for time points at which no value is observed.

Multiple imputation will be performed under the assumption of missing-at-random (MAR) and will be implemented in two steps:

- First, partial imputation assuming MAR will be carried out to impute intermittent (non-monotone) missing data based on a multivariate joint Gaussian imputation model using the Markov chain Monte Carlo (MCMC) method. A separate imputation model will be used for each treatment arm. The imputation models will include countries, surgical approach, gender, age, hemodynamic assessments at each time point from Baseline. The MCMC method will be used with multiple chains, 200 burn-in iterations, and a non-informative prior. In case of non-convergence or non-estimability issues, a single model will be considered with treatment arm added as explanatory variable to the model.
- The remaining monotone missing data will be imputed using sequential regression multiple imputation, where a separate regression model is estimated for imputation of each variable

(i.e., measurement at each time point). Each regression model will include explanatory variables for country, surgical approach, gender, age, treatment and all previous values of hemodynamic assessment from baseline.

No rounding or range restrictions will be applied to imputed continuous values.

Imputed data will consist of 200 imputed datasets. The random seed number for partial imputation with the MCMC method will be 200582, and the random seed number for the sequential regression multiple imputation will be 4112.

Each of the 200 imputed datasets will be analyzed using observed and imputed data.

Change in hemodynamic assessment from baseline to 1-year (5-year) visit will be analyzed by means of a mixed regression model analysis including the treatment, hemodynamic assessment at baseline, country, surgical approach, gender, and age.

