Treatment group comparison at Visit T will be based on the least squares mean (LSM) difference between treatment groups in change from baseline in hemodynamic assessment estimated by the analysis model in each of the imputed datasets. Results from analysis of each imputed dataset, i.e., LSM treatment differences and their standard errors, will be combined using Rubin's imputation rules to produce a pooled LSM estimate of treatment difference, its 95% confidence interval, and a pooled p-value for the test of null hypothesis of no treatment effect.

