Descriptive statistics of the change from baseline of the QALY and EQ-5D index values (continuous) at each FU assessment will be shown as described in section 5.2.

Linear mixed model for repeated measures (MMRM) will be applied to compare EQ-5D index values between the two groups. EQ-5D index values will be adjusted by baseline index value, time point, and treatment-by-time interaction. Patient will be also added to the model as a random variable. Estimates of the least square means for EQ-5D index values and 95 % confidence intervals (CIs) will be calculated by each visit and group.

Descriptive statistics of the change from baseline of the EQ VAS data (continuous) at each FU assessment will be shown as described in section 5.2.

Mann-Whitney tests will be applied to compare treatments in terms of EQ-5D index values and EQ VAS data.

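### SAP 18.2 sets change from baseline as baseline minus later value, so signed laboratory, haemodynamic and EQ-5D changes, and the haemodynamic treatment difference in change, would print with the sign reversed

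*SAP*

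**What the plan says.** SAP 18.2 gives two rules that apply "If not differently indicated".

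- Between arms: "for differences between active and comparator, active will constitute the minuend and comparator the subtrahend".
- Over time: "for changes from baseline the baseline value will constitute the minuend and the later value the subtrahend".

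Three analysis sections depend on the second rule.

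- SAP 13.2 (laboratory parameters) cites it by number: "summary of the change from preoperative assessment, calculated for continuous variables as difference of values (section 18.2").
- SAP 11.2.1 (haemodynamic data) analyses "Mean changes from baseline in site-reported valve hemodynamic" measures, namely mean gradient, peak gradient and LV mass. It bases the comparison of arms on the "least squares mean (LSM) difference between treatment groups in change from baseline in hemodynamic assessment estimated by the analysis model" and pools this over the imputed datasets, with a 95% confidence interval and p-value. It states no order of subtraction.
- SAP 12.3 (health status) plans "Descriptive statistics of the change from baseline of the QALY and EQ-5D index values (continuous) at each FU assessment", and the same for EQ VAS, again with no order stated.

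Neither the SAP nor the protocol defines change as later value minus baseline.

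**The concern.** Readers of a clinical report take a change from baseline as follow-up minus baseline: negative is a fall, positive is a rise. SAP 18.2 prescribes the opposite. Section 18 holds the technical details for implementing the SAP, so a programmer should follow it to the letter.

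The outputs at stake are secondary and safety results. A post-operative fall in haemoglobin would print as positive, a creatinine rise as negative, and a quality-of-life gain as negative. The haemodynamic treatment difference is the most exposed. It is a single model estimate with an interval, and a result favouring Perceval would read as a higher gradient with Perceval. The p-value would be the same either way, so nothing in the test result would reveal the reversal. If some programmers follow 18.2 and others assume the usual order, tables could also disagree in sign with each other.

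**Working it through.** **Inputs.** Write B for the baseline value and L for the later value, with subscripts P (Perceval) and C (control). The two subtraction rules come from SAP 18.2, and the outputs from SAP 11.2.1, 12.3 and 13.2. The plan gives no figure to reproduce. All numerical values below are assumed, for illustration only.

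**Step 1: change within a subject.** Minuend minus subtrahend is the difference, so 18.2 gives change = B − L. The usual definition is L − B, and B − L = −(L − B).

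| Assumed values | SAP 18.2 (B − L) | Usual (L − B) |
|---|---|---|
| Platelets 220 to 150 | 220 − 150 = +70 | −70 |
| EQ-5D index 0.70 to 0.85 | 0.70 − 0.85 = −0.15 | +0.15 |
| Mean gradient 45 to 10 mmHg | 45 − 10 = +35 | −35 |

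**Step 2: treatment difference in change.** The between-arm rule is active minus comparator.

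- SAP 18.2: (B_P − L_P) − (B_C − L_C)
- Usual: (L_P − B_P) − (L_C − B_C)

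The first is the negative of the second. With gradients of 45 to 10 on Perceval and 45 to 13 on control:

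- SAP 18.2: (45 − 10) − (45 − 13) = 35 − 32 = +3
- Usual: (10 − 45) − (13 − 45) = −35 + 32 = −3

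**Step 3: the baseline-adjusted model.** SAP 11.2.1 regresses change on treatment, baseline and other covariates. Negating the outcome negates every coefficient and leaves its standard error alone, so limits (l, u) become (−u, −l). Rubin's rules average the estimates, which negates the pooled value. The within- and between-imputation variances, and so the pooled standard error and two-sided p-value, stay the same.

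A simulated dataset confirms this: 1,000 subjects, 500 per arm, with a true follow-up gradient 2 mmHg lower on Perceval. The model adjusts for baseline.

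| Outcome modelled | Perceval − control | 95% CI | SE |
|---|---|---|---|
| L − B | −1.554 | −2.062 to −1.046 | 0.259 |
| B − L (SAP 18.2) | +1.554 | 1.046 to 2.062 | 0.259 |

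The p-value is identical in the two rows (2.79e-09).

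**Step 4: which outputs are touched.**

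- *Reversed:* numeric changes in continuous laboratory parameters (13.2); changes in mean gradient, peak gradient and LV mass, with their pooled treatment difference (11.2.1); changes in EQ-5D index and EQ VAS (12.3).
- *Not reversed:* laboratory shift tables and the percentage within normal limits (13.2); the Paretian better/worse/same/mixed classes (12.3); the EQ-5D repeated-measures model and the Mann-Whitney comparisons, which use index or VAS values and not changes (12.3); leak severity trends (11.2.2); and the primary analysis, which states its own direction as control minus Perceval (10.2 and 10.3).

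**The case against.** The strongest reply is that a declared sign convention is not a wrong result. The section concerns presentation, the rule is stated openly, and no test, power figure or type I error depends on it. That is right as far as inference goes. It does not remove the problem, because neither 18.2 nor the sections that rely on it require the tables to say which direction is used.

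A second reply is that the levels remain visible. SAP 8.6 shows baseline together with later assessments for echocardiographic values, EQ-5D-5L and blood tests. SAP 13.3 presents platelet counts as levels at each determination. This lessens the risk of misreading the descriptive changes. It does less for the modelled haemodynamic difference, which is reported as one estimate with an interval.

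A third reply is that the outputs themselves cannot be seen. SAP 3.2 records that the list of tables and figures moved to another document and that version 3.0 adopted a new template. The placebo wording in 18.2, in a trial without a placebo arm, fits unedited template text. The wording may be a slip that the programs do not follow; the documents neither show nor exclude this.

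A reader might also infer that every change result is wrong, or that treatment differences in change are reversed for laboratory and EQ-5D data too. The documents do not support either. Many change displays involve no subtraction, and a between-arm difference in change is modelled only for haemodynamics. QALY change is unclear for a separate reason: SAP 12.3 accumulates QALYs from baseline onward, so no baseline QALY is defined to subtract from.

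**Conclusion.** The point holds, within limits. As written, SAP 18.2 defines change as baseline minus later value, and no other provision overrides it. Applied literally, it reverses the sign of every numeric change that defaults to it, and of the pooled haemodynamic difference in change with both confidence limits. The size of each estimate, its standard error and its two-sided p-value are unchanged.

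This is an error of direction in secondary and safety reporting. It does not bear on non-inferiority or any other hypothesis test. The conclusion assumes that the programs follow 18.2 and that the separate table specifications set no other direction, which the two documents do not show. The text of the rule is certain; its effect on the printed tables is conditional on those assumptions.

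**What to change.** In SAP 18.2, swap the two terms so that change from baseline is the later value (minuend) minus the baseline value (subtrahend). Keep active minus comparator for treatment differences. On the tables for 11.2.1, 12.3 and 13.2, add a footnote that a negative change is a decrease, and check the programs against the corrected rule. If the present direction is deliberate, keep it and label the direction on every affected table, including the haemodynamic treatment difference.

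The cost is one sentence in the SAP, footnotes and a programming check. No data collection, sample size or timeline is affected.
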